Management of Uncontrolled Hypertension (HTN)

NCT02922023

10/26/2022

Protocol

1. Title:

Management of Uncontrolled Hypertension: Ambulatory Blood Pressure Monitoring and Subsequent Modification of Therapy or Shifting Anti-hypertensive Medication to Night-time Dosing

2. Investigators:

Principal Investigator:

[name] [name].
Clinical Assistant Professor
Department of Pharmacotherapy and Translational Research

Sub-Investigators:

[name]
[name].
UF College of Pharmacy

[name].
Internal Medicine Physician
UF Health Internal Medicine – Medical Plaza

3. Abstract:

Ambulatory Blood Pressure Monitoring (ABPM) and its role in clinical practice continues to evolve. ABPM allows providers to obtain blood pressure readings over a 24hour period, to assess blood pressure at night to determine “dipping” status, and to evaluate the efficacy of anti-hypertensive therapy. By utilizing ABPM in uncontrolled hypertension patients in clinical practice, modifications in drug therapy can be based on a more comprehensive and accurate depiction of the patient’s overall blood pressure control throughout the day. Although, theoretically, an assessment of the 24-hour blood pressure of a patient prior to adjusting drug therapy should yield better blood pressure control, we would like to carry out a pilot study to investigate whether the modifications in therapy based on ABPM and the resulting impact on blood pressure control would be substantially different from simply switching the dosing of medication to night-time.

In this study, we will compare chronotherapy to ABPM. Data collected will include hypertension drug therapy regimen prior to and during the study, timing of medication administration, and dose, along with the patient’s office blood pressure values prior to study and one month after modification in therapy. This will enable us to explore

whether it is a practical endeavor to implement ABPM as a routine process for all uncontrolled hypertension patients or whether ABPM does not seem to provide considerable value over shifting the timing of drug administration.

4. Background:

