move a medication to bedtime dosing, without relying on ABPM. Given that the initial cost associated with purchasing ABPM equipment (\$2500-\$5000) and software (\$2000-\$3000)¹¹ is not inconsequential, we propose this pilot study to determine whether ABPM in clinical practice is an investment that results in significant difference in blood pressure control when compared with chronotherapy.

5. Specific Aim:

We propose to conduct a pilot study to determine whether the incorporation of Ambulatory Blood Pressure Monitoring (ABPM) as routine procedure in clinic for uncontrolled hypertension influences how anti-hypertensive drug therapy is modified or if simply shifting the dosing of anti-hypertensive medications to night time achieves similar results. We will enroll 20 participants with uncontrolled hypertension, who are prescribed 3 anti-hypertensive medications. All twenty patients will undergo 24-hour blood pressure monitoring with ABPM at baseline and one month after change in therapy has been initiated; ten of the patients will be randomized to receive a shift in dosing schedule of anti-hypertensive medication to night-time without utilizing their ABPM results while the remaining ten will receive modifications in therapy based on their ABPM results and dipping status. The results of this study will assist in assessing the feasibility and benefits of the incorporation of ABPM into the routine management of hypertension.

6. Research Plan:

Patient eligibility

Inclusion criteria

1. Age \geq 18 years
2. Blood pressure of $>130/80$ mmHg
3. Currently receiving 3 anti-hypertensive agents, one of which is a diuretic, for at least six weeks

Exclusion criteria

1. Vulnerable populations
 - a. Pregnant women
 - b. Prisoners
 - c. Cognitively impaired persons
 - d. Economically and/or educationally disadvantaged
 - e. Human fetuses and neonates
 - f. Patients who work night-shift
 - g. Children
 - h. Conditions with visual field deterioration (Anterior Ischemic Optic Neuropathy, Glaucoma, Optic Nerve Disorders)

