
Follow-up will occur for both treatment groups after one month of initiating their modified anti-hypertensive regimen to see how changes in drug therapy impact their blood pressure control. Patients will arrange for their follow-up 24-hour ABPM screening. The procedure from the first ABPM screening will be repeated, and the patient will return the following day to remove the monitor, return their ABPM diary, and submit their ABPM results for analysis.

[figure not shown]

Chart 1: Flow chart demonstrating process for conducting the study

Aside from patients receiving ABPM, all patients will receive standard care in managing their hypertension involving hypertension follow-up appointments and adjustments in therapy to achieve adequate blood pressure control. For those patients who are in the group whose changes in therapy will be determined after evaluating their ABPM results, patients found to be dippers and would not benefit from the switch in dosing to nighttime will receive changes in therapy as would be expected in clinic as standard care if a dose increase/medication change is warranted. Clinical data will be obtained from standard blood pressure monitoring equipment provided by the clinic. Therefore, this study will not result in additional charges associated with the treatment and care of the patient.

Data collection will include age, sex, race, height, weight, comorbidities (Diabetes Mellitus, hyperlipidemia, history of stroke, transient ischemic attack, myocardial infarction, etc.), antihypertensive therapies including dosing schedule at baseline as well as after modification from receiving either treatment option, complete medication history including over-the-counter and herbal medications, whether or not the patient uses a home blood pressure monitor (yes or no), lifestyle history including caffeine and alcohol intake and tobacco use, number of years since HTN diagnosis, whether or not patient was at blood pressure goal at the follow-up visit at one month after initiating change in therapy (yes or no), and the blood pressure readings from the ambulatory blood pressure monitor at baseline and one month post initiation of change in drug therapy. Data will be obtained through EPIC, including the patient-recorded data such as the diary of activity during the 24 hours wearing the ABPM which will be scanned into EPIC. The results of the ABPM will be obtained from the ABPM software and may be scanned into EPIC for ease of access.

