Descriptive statistics, including REDCap (Research Electronic Data Capture) will be used to analyze patient data. Unique patient codes will randomly be assigned to each patient participating in the study through REDCap, and the patient code will serve as the identity of the patient throughout the study. The master list linking the patient codes to the specific patient names will be kept as a physical copy that will remain in a locked filing cabinet in HPNP Room 3313, and only the investigators will have access. The list will be shredded at the conclusion of the study. All electronic files containing clinical information will have PHI removed, and data will be stored on encrypted, password protected files accessed on a UF server. No information will be released to any person or agency without consent of the subject except as required by law.

Analysis plan for initial questions: To determine whether there is a difference in achieving blood pressure goal by using ABPM or chronotherapy.

Descriptive statistics will be carried out using paired t test (changes in blood pressure from baseline vs after 1 month of change in drug therapy for each patient) and Chi-square test or Fisher's Exact Test (amount of subjects from each group that achieved blood pressure goal).

For researchers other than those named on the protocol, use of the data and samples procured under this study will require approval from the PIs of this study in addition to the IRB.

7. Possible Discomforts and Risks:

Risk to the patient from participation in this study is minimal. Participants will not be subjected to processes beyond what is required for obtaining a satisfactory 24-hour blood pressure evaluation and required for routine monitoring of hypertension. Risks of using the ABPM are none. Slight discomfort may occur while wearing the ABPM device throughout the 24 hours as the device periodically inflates, and there may be modest sleep disturbances at the intervals when blood pressure readings are taken. Aside from

the aforementioned, participants will not have any additional discomforts beyond those associated with routine management of their hypertension.

8. Possible Benefits:

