Study subjects may experience benefits from participation in the study if modifications in therapy lead to blood pressure control and achieving patients' blood pressure goals. The results of this study may help to improve anti-hypertensive drug therapy by tailoring and individualizing drug regimens based on patient blood pressure patterns. Results may lead to increased incorporation and use of ABPM in clinical practice and may help us improve how uncontrolled hypertension is treated and managed in clinic, thus providing possible advancements and modifications of protocol in clinic. Therefore, the potential information gained from this study outweighs the minimal risk associated with study participation.

9. Data Safety Monitoring Plan:

Based on assessments of the risk-to-benefit ratio, the risk level associated with the study is minimal. All risks have been described in the consent form.

Monitoring for documentation of an adverse event, whether anticipated or unanticipated, is the responsibility of the principal investigator or co-investigators. Regarding safety monitoring, all adverse events spontaneously reported, elicited, or observed by the investigators will be recorded. All Serious Adverse Events, should they occur, whether study-related or expected, will be documented in REDCap and reported to the IRB within five (5) working days.

In addition, the principal investigator will follow the reporting requirements for serious and unexpected adverse events outlined in the UF IRB Adverse Event Evaluation and Reporting Guide. All unanticipated, serious, fatal and/or life-threatening adverse events will be reported to the UF IRB. Aggregate reports of adverse events will be prepared on an annual basis or at the end of the study, whichever may occur earlier and forwarded to the IRB at annual review.

Plan for data management: Data collection for each subject will be recorded within REDCap. To protect the participant's right of privacy, the master list linking study-assigned patient codes to the patients' personal identifiers will be stored in locked cabinets with limited access, and electronic files will be kept in secured database. A de-identified dataset from the database using a patient identification number will then be shared with statistician for analysis. During the study, data will be analyzed as it becomes available by the PI and co-investigators. No early closure is planned because of the limited scope and projected low risk of the study.

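### The only between-arm analysis is a Chi-square or Fisher test with no planned difference or confidence interval, so it cannot address the part of the aim that asks about similarity

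*Combined protocol and SAP*

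**What the plan says.** The whole analysis stands in a few lines of section 6 (Research Plan) of the combined protocol and SAP.

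- The stated question is "To determine whether there is a difference in achieving blood pressure goal by using ABPM or chronotherapy".
- The first tool is introduced by "Descriptive statistics will be carried out using paired t test". It is applied to each patient's change from baseline, so it is a within-patient comparison.
- The second tool, and the only one that compares the arms, is "Chi-square test or Fisher's Exact Test (amount of subjects from each group that achieved blood pressure goal".
- The outcome is a yes/no item: "whether or not patient was at blood pressure goal at the follow-up visit at one month after initiating change in therapy".

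Section 5 (Specific Aim) sets ten patients per arm. It also asks "if simply shifting the dosing of anti-hypertensive medications to night time achieves similar results". Section 3 (Abstract) offers as one possible conclusion that "ABPM does not seem to provide considerable value over shifting the timing of drug administration". The end of section 4 (Background) asks whether ABPM "is an investment that results in significant difference in blood pressure control when compared with chronotherapy".

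The study is called a pilot and the tests are placed under descriptive statistics. No section gives a significance level, an assumed goal rate, a margin for similarity, a difference in goal rates or a confidence interval.

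**The concern.** The aim has two possible answers: the arms differ, or they do about equally well. The planned test speaks only to the first. With 10 per arm a non-significant result is likely even when the true difference is large, and nothing planned would show how large a difference remains possible. A reader weighing the purchase of ABPM equipment could then take a non-significant test as a sign that ABPM adds little.

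A lesser matter is that the plan names two tests and no rule for choosing between them. One needs to know whether that choice can change a decision, and whether the test that results uses the 20 patients well.

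**Working it through.** **Inputs.** From the documents: 10 patients per arm (section 5), and a binary outcome at one month compared by Chi-square or Fisher (section 6). Assumed, because the documents are silent: a two-sided 5% level; illustrative goal rates of 30% v 60% and 30% v 70%; one to four lost outcomes; and ±30 points as an illustrative yardstick for similarity. The sample size of 20 has no stated derivation, so there is no figure to reproduce.

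**Step 1. What an interval would show.** The Wilson limits for x/n, with p = x/n and z = 1.96, are [p + z²/2n ± z√(p(1-p)/n + z²/4n²)] / (1 + z²/n). For 5/10 the centre is 0.5 and the half-width is 1.96 × √(0.025 + 0.0096) / 1.384 = 0.263, so the limits are 0.237 and 0.763. The lower Newcombe limit for the difference d is d - √[(p1 - l1)² + (u2 - p2)²] = 0 - √(0.263² + 0.263²) = -0.37. The upper limit is +0.37 by symmetry.

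| At goal | Newcombe 95% CI, points |
|---|---|
| 5/10 v 5/10 | -37 to +37 |
| 6/10 v 4/10 | -21 to +53 |
| 7/10 v 3/10 | -3 to +67 |

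All three are non-significant by Fisher (p = 1.00, 0.66 and 0.18).

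**Step 2. All possible results.** At 10 v 10 there are 11 × 11 = 121 tables. Fisher rejects 34, which leaves 87 non-significant. Only two of those 87 (0/10 v 0/10 and 10/10 v 10/10) have an interval wholly within ±30 points. At 8 v 8 the count is 0 of 61.

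**Step 3. How likely a non-significant result is.** At 10 v 10, Fisher's power is 12.3% for 30% v 60% and 24.3% for 30% v 70%. The chance of non-significance is therefore 88% and 76%. With Boschloo's test it is 75% and 58%.

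**Step 4. Does the missing selection rule matter?** Take the usual convention: chi-square only if all four expected counts are at least 5. The expected counts sum to the number of outcomes, so with 19 or fewer the smallest is at most 19/4 = 4.75 and Fisher is always used. With 20, all four reach 5 only when exactly 10 patients are at goal. In those tables the tests decide alike (for 2 v 8, Fisher p = 0.023 and chi-square p = 0.007; for 3 v 7, 0.18 and 0.07). In ordinary use the wording therefore amounts to Fisher.

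**Step 5. Size and power of the candidate tests.** Size is the sum, over the rejected tables, of C(n1,a) C(n2,b) π^(a+b) (1-π)^(N-a-b), maximised over a common goal rate π. Boschloo's p-value is the same maximum taken over the tables whose Fisher p is no larger than the one observed, so it rejects whenever Fisher does. The lower goal rate is placed in the larger arm.

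| Analysed | Max size: Fisher | Boschloo | Uncorrected chi-square | Power 30% v 60%: Fisher | Boschloo |
|---|---|---|---|---|---|
| 10 v 10 | 1.3% | 4.2% | 4.2% | 12.3% | 24.8% |
| 10 v 9 | 2.1% | 3.6% | 6.5% | 16.0% | 20.3% |
| 9 v 9 | 2.1% | 3.3% | 5.7% | 14.4% | 19.5% |
| 10 v 8 | 2.5% | 4.6% | 5.3% | 15.4% | 22.4% |
| 8 v 8 | 2.1% | 2.8% | 7.7% | 13.3% | 14.8% |

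At 10 v 10, Boschloo rejects 46 tables: Fisher's 34 and 12 more. One of the 12 is 7/10 v 2/10 (Fisher p = 0.070, Boschloo p = 0.041, Newcombe CI +7 to +74 points).

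**The case against.** The strongest reply is that the plan draws no wrong inference. Its stated analysis question is about a difference, a two-sided test matches that question, the study is a pilot, and the tests are labelled descriptive. All of this stands. A reader might infer that the investigators mean to read non-significance as similarity; no section says so. The criticism is narrower: one part of the aim has no analysis that could address it. The descriptive label favours an estimate with an interval rather than excusing its absence.

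The numbers at goal in each arm will presumably be reported, so a reader could work out the interval. That is fair, and the plan should not be described as promising nothing but a p-value. It is still better to commit to the estimate in advance.

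A reader might also take Fisher's 1.3% for an error, or suppose that the open choice of test distorts the result. Neither is supported. Fisher controls the type I error, 1.3% is a maximum that needs complete 10 v 10 data, and in ordinary use the choice changes no decision. Boschloo's gain is fragile: at 30% v 60% it falls from 12.5 points with complete data (24.8 - 12.3) to 4.3 with one lost outcome (20.3 - 16.0) and 1.5 at 8 v 8 (14.8 - 13.3). The outcome needs a return visit, so losses are plausible.

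Section 8 (Possible Benefits) says "Results may lead to increased incorporation and use of ABPM in clinical practice". That is conditional and describes a result in favour of ABPM. It gives little support to the idea that a null result would be misused.

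Finally, the two ABPM recordings would allow a between-arm comparison of continuous changes. That is a separate matter and does not remove the need for an interval on the comparison that is planned.

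**Conclusion.** The point holds as a reporting gap in the main comparison. The sole between-arm analysis has no planned estimate or interval, and a test at 10 per arm cannot speak to similarity: equal arms at 5/10 leave ±37 points open, and 2 of 87 non-significant tables fall within ±30 points. The intervals themselves need no assumed goal rates. The table counts, sizes and powers assume a two-sided 5% level, the powers also rest on illustrative goal rates, and ±30 points is a yardstick chosen here.

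The choice of test is secondary. Fisher is acceptable and conservative. Boschloo is at least as powerful, markedly so only with complete data. Uncorrected chi-square is the one option to rule out, since its size passes 5% once outcomes are missing.

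**What to change.** 1. **Main change.** In the analysis plan of section 6, make the difference in goal rates with a Newcombe 95% confidence interval the main between-arm result. State that a non-significant result is inconclusive and does not show that the two approaches perform alike.
2. **Secondary change.** Replace the choice of two tests by one named in advance, at a stated level (two-sided 5% assumed here). Boschloo is preferable and Fisher alone is valid; uncorrected chi-square should not be used. Add that the named test decides significance if test and interval disagree.

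The cost is wording only, with no extra patients or data. The downsides are a less familiar test, a more modest claim and an approximate interval (at 10 v 10, coverage averages 95.3% over goal rates from 2% to 98%, with a minimum of 88%). Boschloo and the Newcombe interval agree in all 121 tables at 10 v 10, but disagree in 6 of 110 at 10 v 9 and 6 of 81 at 8 v 8. If Fisher is kept, they disagree in 12 of 121 at 10 v 10 (46 - 34), which is why the tie-break sentence is needed. None of this makes a 20-patient pilot adequately powered.

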ABPM is primarily used to diagnose white coat hypertension, however, ABPM may be used to assess efficacy of blood pressure treatment by evaluating the patient's blood pressure control over a 24-hour period.⁵ The capability to provide night-time readings during sleep sets it apart from office blood pressure readings and home blood pressure readings, and it provides information for the determination of dipping status. Non-dipping status has been associated with target organ damage including left ventricular hypertrophy, microalbuminuria, cerebrovascular disease, congestive heart failure, vascular dementia, stroke, and myocardial infarction.⁶ The frequency of non-dipper patterns tends to be higher in hypertension that is secondary to specific medical conditions such as chronic renal failure, diabetes, and autonomic nervous system dysfunction than in uncomplicated primary hypertension. A study also showed that the percentage of patients that ingest all their antihypertensive medications in the morning was significantly greater in non-dippers than the dippers suggesting that non-dipping among treated patients is partly due to lack of 24-hour therapeutic coverage when administered in the morning.⁹

stages hypertension as Stage 1 with pressure. Adults between the ages of 18 and 59 years old or any adult with diabetes or chronic kidney disease are considered hypertensive with three consecutive blood pressure readings above 140/90 mmHg.⁷ Resistant hypertension is defined as blood pressure that remains above the goal of 130/80 mmHg despite the use of three anti-hypertensive agents at optimal doses including a diuretic, if possible, or blood pressure that is controlled with the use of four or more antihypertensive drugs.⁸ Although non-adherence is a common contributing factor to pseudo-resistant hypertension, it remains difficult to apply a simple, inexpensive, and reliable method in the clinical setting to quantify this factor when investigating potential causes for resistant hypertension.⁸ Additionally, seemingly resistant hypertension may be related to inadequate night-time blood pressure control leading to elevated blood pressures during sleep as well as a higher-than-normal morning rise/spike upon awakening.⁶

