Chronotherapy is the purposeful timing of medications to synchronize drug concentrations with established circadian rhythms in an effort to enhance treatment outcomes and prevent adverse effects.⁶ Chronotherapy of anti-hypertensive medications has been used to attenuate morning rise of systolic and diastolic blood pressure, normalize elevated daytime, nighttime, and 24-hour blood pressure means, and convert abnormal 24-hour blood pressure profiles to normal dipping patterns. Tailoring medication levels in close synchrony with known and expected day-night patterns in both systolic and diastolic blood pressure can optimize the drug's effects.⁹ Given that optimal anti-hypertensive drug therapy may be dependent on circadian rhythms, dipping status, and individual 24-hour blood pressure patterns, along with the fact that ABPM serves as one of the only ways to easily evaluate a patient's blood pressure patterns throughout the day and night, we are interested in investigating whether ABPM is beneficial in clinical practice.

There are potential risks for dosing antihypertensive medications at bedtime in patients with visual field deterioration. A study which investigated 24-hour ABPM in patients with anterior ischemic optic neuropathy (AION), glaucoma, and other optic nerve head disorders have shown a 26% reduction in systolic blood pressure and 33% reduction in diastolic blood pressure at night.¹² Patients with a progressive visual field deterioration had significantly greater mean decreases in systolic blood pressure from daytime readings (46.8 ± 2.5 mmHg) compared to those without deterioration (35.0 ± 3.1 mmHg).¹² Based on these and other studies, it was hypothesized that nocturnal hypotension may lead to ischemia of the anterior ciliary artery and reduce optic nerve head blood flow below a crucial level in certain vulnerable patients triggering the precipitation of AION and blindness.¹³ Therefore, patients with visual field deterioration should be excluded from the study to prevent the possibility of developing AION.

Clinical application of ABPM may lead providers to add a new drug if the patient is a dipper or shift the dosing of an existing medication to night-time, or add a dose of an existing medication to bedtime. However, it is also possible that providers could simply

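### The analysis plan names no sleep-time pressure or dipping outcome, leaves the t test's blood pressure undefined, and compares the arms only on yes/no goal attainment

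*Combined protocol and SAP*

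**What the plan says.** **Rationale (section 4, Background).** Absence of dipping is linked to target organ damage, and apparent resistance to treatment may reflect poor night-time control. Chronotherapy is said, among other uses, to "convert abnormal 24-hour blood pressure profiles to normal dipping patterns". On ABPM the text says: "The capability to provide night-time readings during sleep sets it apart from office blood pressure readings and home blood pressure readings". The same section warns that nocturnal hypotension may harm the optic nerve in vulnerable patients.

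**Treatment (section 6).** Every chronotherapy patient has one drug moved to night without the ABPM being consulted. In the ABPM arm, non-dippers also have a drug moved to night, while dippers get a standard-care regimen change.

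**Data (section 6).** The data list includes "the blood pressure readings from the ambulatory blood pressure monitor at baseline and one month post initiation of change in drug therapy". A diary records bedtime and awakening. A satisfactory recording needs at least 20 daytime and 7 asleep readings. Goal status is collected as "whether or not patient was at blood pressure goal at the follow-up visit at one month after initiating change in therapy (yes or no").

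**Analysis (section 6).** The paired t test is on "changes in blood pressure from baseline vs after 1 month of change in drug therapy for each patient". The Chi-square or Fisher test is on the "amount of subjects from each group that achieved blood pressure goal".

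**Source of the pressure.** The Abstract (section 3) lists "office blood pressure values prior to study and one month after modification in therapy". Section 6 adds: "Clinical data will be obtained from standard blood pressure monitoring equipment provided by the clinic". Section 6 also has patients hand in their follow-up ABPM results for analysis. The analysis plan does not say which of these it uses.

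**The concern.** The trial is argued largely from night-time pressure and measures it twice in each patient, but the analysis plan does not name it as an outcome. Three gaps combine:

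- The t test's variable is open: office or ABPM; 24-hour, awake or asleep; systolic or diastolic.
- The t test is within-patient. Even if it used asleep values, it would not compare the arms.
- The one between-arm comparison is a yes/no status at a visit, against a goal that the analysis plan does not define.

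The Abstract intends to judge whether ABPM adds considerable value over a timing shift. A null result on goal attainment could be read as equivalence while night pressure differs between arms. An excessive nocturnal fall could go unnoticed. Leaving the variable open also allows it to be chosen after results are seen, and section 9 has the investigators analysing data while the study runs.

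**Working it through.** **1. The plan's own figures.** There is no alpha, power, SD or effect size to reproduce. The only figure is the sample size, 10 + 10 = 20, which agrees.

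**2. How much of a sleep-only change each measure carries.** Assume 16 h awake and 8 h asleep.

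- 24-hour mean change = (16 × awake change + 8 × asleep change) / 24.
- A 10 mmHg asleep fall with no awake change gives 8 × 10 / 24 = 3.3 mmHg, or 33%.
- Averaging readings at the protocol's minimum counts instead gives a weight of 7/27 = 26%, so 10 mmHg becomes 2.6 mmHg.
- A daytime office reading moves by 0 by construction.

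Example: awake 140, asleep 136 falling to 126. The decline, (awake − asleep)/awake, goes from 2.9% to 10.0%. The 24-hour mean goes only from 138.7 to 135.3. This patient starts as a non-dipper and would have a drug moved to night in either arm, so the example shows dilution, not an arm difference.

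**3. Where the arms differ: dippers.** Take a dipper at 140 awake and 126 asleep (10.0% decline; 24-hour mean (16 × 140 + 8 × 126)/24 = 135.3). All changes below are assumed.

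| One-month state | Awake | Asleep | 24-hour mean | Decline |
|---|---|---|---|---|
| Drug moved to night; fall confined to sleep | 140 | 112 | 130.7 | 20.0% |
| Regimen change; proportional fall, factor 130.67/135.33 = 0.9655 | 135.2 | 121.7 | 130.7 | 10.0% |

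The 24-hour means are equal, and neither patient is below 130 systolic on awake or 24-hour values. (The 130/80 figure is from the Background's definition of resistant hypertension; the analysis plan sets no goal.) Asleep pressure differs by 121.7 − 112 = 9.7 mmHg. In the first row, a 14 mmHg night fall appears as a 4.7 mmHg better 24-hour mean.

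The second row also shows why percent decline is a poor efficacy measure here: a proportional reduction leaves it at 10.0%.

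**4. Precision at 10 per arm.** SD of change is assumed to be 8 to 15 mmHg, two-sided 5%.

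- Power for a 10 mmHg between-arm difference in asleep mean: 0.75 (SD 8) to 0.29 (SD 15).
- Power for the same effect diluted to 3.3 or 2.6 mmHg, with the same SDs: 0.14 (3.3 mmHg, SD 8) to 0.07 (2.6 mmHg, SD 15). A 24-hour mean may have a smaller SD, which would narrow this gap.
- Fisher test on goal attainment: 0.12 for 30% v 60%, and 0.24 for 30% v 70% (assumed rates).
- 95% interval half-width for an unadjusted difference: 2.101 × SD × √(2/10) = 0.94 × SD, or 7.5 to 14.1 mmHg.

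**The case against.** **Night pressure may already be the t test's variable.** A reader might infer that neither planned outcome measures it. The documents do not support that. Source and period are unstated, ABPM readings are collected at both times and handed in for analysis, and asleep readings are required for validity. This objection stands: the defect is under-specification, not proven absence. It does not supply a between-arm comparison, because the t test is within-patient.

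**Non-dippers do not separate the arms.** A reader might take any improvement in a non-dipper's dipping as an arm difference that the plan would miss. Non-dippers get the same type of change in both arms, so counting conversions to dipper by arm would compare like with like. This stands, and the divergence is mainly in dippers.

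**The treatment is not aimed only at sleep.** The Background also credits chronotherapy with lowering daytime and 24-hour means and blunting the morning rise. That moving a drug simply trades day effect for night effect is an assumption. The stated question is goal attainment. All of this supports keeping that outcome, but it does not argue against reporting asleep pressure too.

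**Safety is not ignored.** Conditions with visual field deterioration are excluded, diaries record symptoms, and observed adverse events are recorded. This stands in part, but no summary of low night readings is planned, including for dippers moved to night dosing without their ABPM being consulted.

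**Not every recording will be usable.** Some may miss the validity minimums, so asleep data in all 20 patients cannot be assumed.

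**Conclusion.** The concern holds in limited form. The plan does not specify sleep-time pressure or dipping as an outcome, does not say which pressure the t test uses, and compares the arms only on a yes/no goal. A sleep-only change would be invisible in daytime office pressure and reduced to about one third in a 24-hour mean (26% to 33% across the two weightings). Among dippers, a larger nocturnal fall in one arm could be missed or counted as better control.

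The sizes rest on an assumed 8 h of sleep and on illustrative pressures, changes and SDs. No figure in the documents is contradicted. This is an inexpensive improvement to a pilot, not a flaw that invalidates it.

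**What to change.** In the analysis plan of section 6:

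1. Keep goal attainment, and name the blood pressure used in each analysis (source, period, systolic or diastolic).
2. Add a between-arm comparison of one-month asleep mean systolic and diastolic pressure, adjusted for the baseline value of the same measure. Take the asleep period from the diary and use recordings that meet the section 6 validity minimums. Report the estimate with a confidence interval, alongside the awake and 24-hour means.
3. Report percent sleep-time decline descriptively, by arm and by baseline dipping status, and not as an efficacy outcome.
4. Report the distribution of nocturnal falls by arm as a descriptive safety result. Any clinical threshold is for the investigators to set.

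The cost is protocol wording and a little analysis; the recordings and diary are already planned. The downside is a few more estimates in a 20-patient pilot, with wide intervals and possibly some invalid recordings.
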